We have also taken steps to enhance PCP acceptance of the intervention: a) high-level support from UPMC Health Plan, PCP network (Community Medicine Incorporated, including 90 practices and 330 PCPs), and the Nephrology Division; b) meeting with lead physicians and refining the intervention to harmonize with workflow; c) documenting PCP responses in the EHR; d) ongoing communication with PCP groups and leadership.

Electronic nephrology consult. Orders for e-consults will be received in an electronic basket monitored by the study coordinator. The consults will be routed to 1 of 12 board certified nephrology clinicians, who will undergo training to standardize consult focus and communication. The notes will adopt a "Situation, Background, Assessment, Recommendation"94-97 template to ensure clear, concise communication. The note will be completed at least several days prior to the patient's appointment and routed to the PCP's message basket and documented in the chart to allow time for review and clarification. The initial consult will focus primarily on HTN control, proteinuria assessment and suppression, RAASi use, and medication safety. The note will include a bolded list of recommendations with orders placed in a pended status (i.e., entered, but awaiting acceptance from the PCP). To enhance communication and care coordination, the e-consultant will ensure CKD is added to the problem list. 98 In addition, the problem list will convey that the patient is followed by the e-consult team, reachable via listed message baskets and phone numbers. The nephrologist will include an order for remote electronic follow-up, which will be captured in the PHM dashboard. Electronic messages will be sent to the nephrologist to perform the follow-up approximately 3 weeks before the recommended interval. When necessary, traditional office evaluations will be suggested.

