### VI. Regulatory and Oversight Considerations

This study meets the criteria for human subject's research.

We will conduct a cluster RCT of PCP practices, implementing a multifaceted PHM intervention for patients with high-risk CKD. The intervention targets improvements in the delivery of evidence-based care and outcomes. Patients with high-risk CKD will be identified through demographics and laboratory tests that are collected for clinical purposes. The PHM dashboard, which includes estimates from validated risk prediction models and eGFR trajectories, will be used to identify and track enrolled patients. Shortly before their regularly scheduled visit with an enrolled patient, PCPs randomized to the intervention arm will receive a decision support message and subsequent reminders notifying the provider of the patient's high-risk CKD status and recommending the following bundle: 1) an order for electronic nephrology guidance or formal nephrology office consultation if preferred; 2) medication therapy management by a PharmD, specifically including a medication reconciliation and safety review, and 3) CKD patient education. These interventions are all consistent with standard of care practices for patients with high-risk CKD and the PCP will always be permitted to accept or refuse these suggestions according to their clinical judgement. If the provider accepts these suggestions, the individual intervention components will be ordered, scheduled, coordinated, and tracked. If the provider refuses any of the components, they will be able to justify why their reasons for refusal. Refusal responses will be randomly audited to ensure accuracy.

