### a. Potential Risk:

PCPs will be at minimal risk with regards to their reputation, finances, legal liability, or position in their department or practice. Their exposure is limited to intermittent outreach from the investigators and EHR communications/reminders regarding their enrolled patients. These messages will recommend evidence-based care (e.g., implementation of RAASi, avoidance of NSAIDs, checking a urinary albumin to creatinine ratio) for a high-risk CKD population. The provider can then choose to enact or ignore the suggestions, and document reasons for refusal. The messages and communication have been designed to activate in a manner that harmonizes with existing PCP workflow. Processing these messages should require far less than 1 minute per patient, exposing the PCPs to a minimal risk of temporal inconvenience. Assuming a uniform distribution of high-risk CKD patients throughout the practices, the average PCP will have ~5 patients included in the study.

However, because patient distribution is not uniform, we estimate a single PCP may have up to ~15 patients in the study. This will still pose a minimal temporal burden over the course of the trial.

All data analysis on provider performance will be reported in the aggregate; hence, performance of an individual PCP will not be identifiable. In the unlikely event of a breach of confidentiality, the physicians will be exposed to minimal risks to their reputation, job security/finances, or legal liability as physician data will be strictly de-identified with a password protected "key" stored separately in a password protected file on a secure university server. Even if the key was stolen (which we deem to be very unlikely to happen), the data regarding physicians would be of limited implication as there are no formal metrics regarding CKD care and we will not gather any high-risk provider information (e.g., dob, SSN, etc). Alternative treatments at this time are to continue usual care (e.g., continuing medical education activities to PCPs) which has proven ineffective in optimizing PCP performance including treatment of CKD.

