This study will also subject the enrolled patients of participating providers to minimal risks. At baseline, enrolled patients are at high-risk for poor outcomes including catastrophic outcomes such as ESRD. The predictive models used to make these estimates have been externally validated in multiple populations. When the PCP accepts the recommended intervention bundle the following events will occur. First, electronic nephrology guidance will

be provided, which will give the PCP recommendations on how to improve CKD related care prior to their visit with the patient. This intervention is strictly provider facing (i.e., the patient is not contacted by the nephrologist). The PHM dashboard will be used to track whether recommendations are implemented and to send reminder messages to PCPs unless reasons for non-implementation are provided. Second, the patient will have a telephonic appointment made with a PharmD to review their medications. If an emergent medication hazard is discovered, the PharmD will ask the patient to hold the offending medication(s) and will immediately contact PIs, and the patient's PCP. These emergent events are likely to be guite infrequent. Otherwise, following completion of the medication reconciliation and safety review, the pharmacist's findings will be reported to the PCP so that they may be reviewed with the patient and appropriate changes made (in accordance with the PCP's clinical judgement). Third, the patient will be scheduled for a CKD nurse education session following their appointment with their PCP (thereby allowing the PCP to share the CKD diagnosis with the patient). The nurse education session will provide information on the role of the kidneys, kidney function assessment, strategies to protect kidney function, medication safety, and general information about ESRD treatment options. Given patients' high-risk CKD status, CKD education is considered standard of care and patients may opt out of the education session if they find it distressing.

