Secondary process of care outcomes (Aim 1): To assess the intervention effect on hypertension control, we will compare the mean outpatient systolic blood pressure (SBP) between intervention and control at each 6-month time point using LMM with fixed effects for treatment, time, and treatment by time interaction. At each time point, the average of all BP measurements within a +/- 3-month window will be used to account for random fluctuations. As an alternative approach, we will analyze BP as a binary outcome defined by achieving BP goal of <140/90 mm Hg or <130/80 mm Hg via GLMM with logit link and binomial family. If linearity of time is reasonable, we will compare the slopes between intervention and control. These models will include random patient intercepts nested within random practice intercepts and will be adjusted for pre-specified covariates (age, sex, race, and practice size). In examining medication use, we will compare the average medication exposure days between the arms using LMM with random practice effect. For each medication class, the number of exposure days will be determined by counting the number of days from medication order start date to either the discontinuation date, survival endpoint date (progression, ESKD, death/hospice, MMWD) or study end date, whichever comes first. (refer to Table 1 for details). To account for potential overdispersion, we will also fit count models including Poisson, generalized Poisson, and negative binomial mixed models and select the final model based on minimum Akaike Information Criteria (AIC) or Bayesian Information Criteria (BIC). If count models provide better fit, we will report the rate of exposure days per year for each medication. We will adjust for baseline medication exposure days in addition to pre-specified covariates with the log of the number follow-up days as offset. In post-hoc analyses, we will evaluate the effect of intervention on albuminuria minimization among patients with at least one urine-albumin-tocreatinine ratio (UACR) measure during the study period. Similar to the approach we used for examining changes in eGFR, we will fit a mixed effects model utilizing all available UACR for each patient adjusting for age, sex, race, baseline eGFR and practice size. We will also adjust for diabetes since we found that it is associated with having at least one UACR measure during the study period. Changes in UACR from baseline to 18 months (approximately the median follow-up time) were calculated by group, and between group differences were compared using contrasts.

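### The post-hoc UACR comparison includes only patients tested during the study, the intervention promotes that test in one arm, and the SAP does not say that testing is compared by arm or that untested patients are covered

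*Combined protocol and SAP*

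**What the plan says.** In the final SAP, the paragraph on secondary process-of-care outcomes restricts the post-hoc albuminuria analysis to a subset: "among patients with at least one urine-albumin-tocreatinine ratio (UACR) measure during the study period". A mixed model uses every available UACR of those patients, adjusted for age, sex, race, baseline eGFR and practice size. One further covariate is explained: "We will also adjust for diabetes since we found that it is associated with having at least one UACR measure during the study period". The contrast is then described as already done: "Changes in UACR from baseline to 18 months (approximately the median follow-up time) were calculated by group", with the groups compared.

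Four places in the protocol describe what the intervention does to testing:

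- Section VI: "PCPs randomized to the intervention arm will receive a decision support message and subsequent reminders notifying the provider" of high-risk status and recommending the bundle.
- Section VI, potential risk: the messages recommend evidence-based care, and one example given is "checking a urinary albumin to creatinine ratio".
- Section IV, electronic nephrology consult: the initial consult concentrates on several topics, including "proteinuria assessment and suppression", and recommendations come with "orders placed in a pended status".
- Section VI, potential risk: the dashboard is used "to send reminder messages to PCPs unless reasons for non-implementation are provided".

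Section IV leaves usual-care patients on their existing care. The yearly alert to PCPs in both arms (final SAP, clinical outcome) asks for a BMP, which contains no urine albumin.

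The final SAP also has general provisions: descriptive summaries by arm, baseline levels among the adjustment covariates, and a missing-data section that names multiple imputation, selection models and pattern-mixture models.

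**The concern.** Randomisation makes the two arms comparable as enrolled. It does not make the tested patients of one arm comparable with the tested patients of the other when one arm is prompted to test. If extra prompting brings in patients whom usual care would not have tested, the tested groups can differ in starting level and in regression to the mean. A change contrast can then move with no effect on albuminuria.

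The plan accepts this reasoning for eGFR. The original SAP names ascertainment bias from more frequent measurement in the intervention arm, and the final SAP keeps window averaging and the BMP alert partly for that reason. UACR has no such safeguard, and averaging could not bring back patients who have no value at all.

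What is at stake is how the UACR result is read: as a drop in albuminuria, as no effect, or as a by-product of who was tested.

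**Working it through.** The documents give no UACR testing rate, UACR variance or target effect, so there is no figure of the plan to reproduce. The check has a textual part and an illustration in which every input is assumed.

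**Textual part.** Three statements have to hold together, and they do. Entry depends on a test after randomisation (final SAP). The test is encouraged in the intervention arm only (protocol sections IV and VI; the both-arm alert is for a BMP). No stated step is both specific to UACR and specific to arm: the diabetes covariate is specific to UACR but not to arm, and the missing-data section names neither. The SAP found diabetes to predict testing, but does not say whether arm was among the predictors examined.

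**Illustration.** Assume no true effect and one baseline/follow-up pair of log UACR per patient, with standard deviation SD and repeat correlation r. A patient is tested when a latent normal variable exceeds a threshold. That variable has correlation rho with W, where W is baseline, stable or current log UACR. Let p be the share tested and λ(p) = φ(z)/p with z = Φ⁻¹(1 − p). Then

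- d = rho × [λ(pI) − λ(pC)]
- bias in log change among the tested: −(1 − r)·SD·d if W is baseline; +(1 − r)·SD·d if W is current; 0 if W is the stable level, because selection then moves both values equally.

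With rho = 0.5, SD = 1.5, r = 0.7 and pC = 0.5: λ(0.5) = 0.7979 and λ(0.7) = 0.4967, so d = 0.5 × (0.4967 − 0.7979) = −0.1506. The size of the bias is 0.3 × 1.5 × 0.1506 = 0.0678 on the log scale.

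| Tested, usual care v intervention | d | Follows baseline | Follows stable level | Follows current |
|---|---|---|---|---|
| 50% v 60% | −0.0770 | +3.5% | 0 | −3.4% |
| 50% v 70% | −0.1506 | +7.0% | 0 | −6.6% |
| 50% v 80% | −0.2240 | +10.6% | 0 | −9.6% |

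- Equal testing with the same pattern in both arms gives zero.
- At rho = 0.3 the sizes fall to about 2%, 4% and 6%.
- At 50% v 70%, SD 1.0 with r 0.8 gives +3.1%/−3.0%, and SD 1.8 with r 0.6 gives +11.4%/−10.3%.
- A different selection model, in which testing depends on the UACR change itself through a logistic curve, gave false ratios of about 0.95 to 0.85 at 50% v 70%. The size depends on the assumed mechanism.

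**Precision.** With 825 patients per arm (1,650/2), SE = √[2 × 0.3 × 1.5² × (1/412.5 + 1/577.5)] = √(1.35 × 0.004156) = 0.075. A bias of 0.068 is about 0.9 SE. That would raise a nominal 5% false-positive rate to about 15%.

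**Check of remedies** (simulation, 4 million per arm, 50% v 70%, SD 1.5, r 0.7):

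| Testing follows | Planned contrast | Imputation on baseline within arm, no shift | Baseline covariate among the tested | Shift ratio that makes imputed values right |
|---|---|---|---|---|
| Baseline | +7% | 0% | 0% | 1.00 |
| Stable level | 0% | −6% | −6% | 0.71 |
| Current | −7% | −12% | −12% | 0.51–0.52 |

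When testing follows the current value, the required shift is about 0.45 at SD 1.8, r 0.7, and about 0.37 at SD 1.8, r 0.6. A range that stops at 0.5 would miss these cases.

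**The case against.** The strongest reply is that the SAP already covers this. Its missing-data section is not limited to particular outcomes. It promises a description of missingness, an enquiry into its causes, and imputation and pattern-mixture methods. The diabetes covariate looks like that section applied to UACR. Summaries by arm are also planned. All of this stands, so a reader who inferred that the plan has no adjustment or no missing-data strategy would be wrong. What remains is narrower: nothing ties those methods to patients whom the analysis set removes, or says that testing is compared by arm. A mixed model that copes with values missing at random does so for the patients in it, and a diabetes covariate removes only the selection that diabetes explains.

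Second, exposure to prompting may be modest. UACR is one example among several, PCPs may ignore suggestions, and reminders can be ended by giving a reason. One might infer that reminders run until the test is done, but the protocol does not say that.

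Third, the analysis is labelled post hoc, and the SAP discloses that it followed the unveiling of results and a reviewer's suggestion. That is correct, and no further label is needed.

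Fourth, size and sign are unknown, and the one-pair illustration is not the planned mixed model. That also stands.

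**Conclusion.** The point holds as a minor one. The UACR contrast rests on a set of patients formed after randomisation by an event that one arm is encouraged to have, and the SAP states no comparison of testing by arm. The documents do not show that testing differed or that the result is biased. A reader might infer a spurious albuminuria benefit, but the distortion can equally hide one, and it is zero if testing follows the stable level or is equal and alike in both arms.

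The range of about −10% to +11% at 50% v 70% tested rests entirely on assumed testing rates, SD, repeat correlation and testing correlation. The negative end assumes testing that follows the current UACR, which is an outer case because that value is unknown before the test. The consequence is confined to how the UACR result is interpreted.

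**What to change.** 1. Report by arm the share of patients with a UACR after T0, tests per patient-year, and baseline UACR and eGFR of tested and untested patients.
2. Keep the planned contrast. Beside it, add one sensitivity analysis in all randomised patients, using the multiple imputation and pattern-mixture methods that the SAP already names. Put arm and baseline UACR in the imputation model. Apply a ratio shift to the imputed values of untested patients, separately by arm if testing differs. Vary it from no shift until the conclusion changes, or at least down to a ratio of about 0.35.
3. If the conclusion changes within that range, or testing differs clearly by arm, state that the UACR result may reflect selective testing and is not evidence of an effect on albuminuria.

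Do not replace the main model with one adjusted for baseline UACR among the tested. In the illustration it is further from zero than the planned contrast in two of the three mechanisms. If that model is run, report it only as a further sensitivity analysis.

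The cost is one table and one extra analysis. Baselines converted from protein or dipstick results (SAP Table 1) add noise, and patients with no baseline UACR need theirs imputed too. No single method removes the selection under every testing mechanism, which is why a range is shown beside the planned contrast.

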# III. Study Objectives

The overarching aim of the Kidney Coordinated HeAlth Management Partnership (Kidney CHAMP) trial is to test the effectiveness of a multifaceted EHR-based PHM intervention to improve evidence-based CKD care in high-risk patients in a highly pragmatic, cluster randomized trial (CRT). By combining timely nephrology guidance, pharmacist-led medication management services, and CKD patient education, our intervention will improve CKD risk stratification, resource allocation, adoption of evidence-based interventions, and medication safety and efficacy, while minimizing the PCP and patient burden

Aim 1: To perform a 42-month pragmatic, cluster RCT comparing the effect of an EHR-based PHM intervention versus usual care on key processes of care in 1,700 high-risk CKD patients.

Aim 1a: To examine the effect of the intervention on systolic blood pressure (SBP) in HTN patients.

Aim 1b: To examine the effect of the intervention on RAASi use in albuminuric patients. Aim 1c: To examine the effect of the intervention on exposures to potentially unsafe medications.

Aim 2: To test the clinical effectiveness of a multifaceted PHM intervention in reducing kidney disease progression in 1,700 high-risk CKD patients enrolled in a 42-month pragmatic, cluster RCT.

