### **Final Statistical Analysis Plan**

Clinical outcome (primary study outcome): A ≥40% decline in eGFR or ESRD.(1) eGFR decline will be adjudicated based on the baseline creatinine and eGFR determined from the CKD-EPI creatinine (2021) equation.(6). To limit ascertainment bias, we will also use a once yearly decision support alert to remind

study PCPs in both arms to order a BMP on study patients, if results are not available in the last 6 months. ESRD will be defined as an eGFR < 10ml/min to account for patients with markedly reduced baseline eGFR values (i.e., 16-20ml/min). To limit surveillance bias, in addition to the above alert, we will use 6-month ascertainment windows and average all values within each window. (Table 1). Researchers involved in outcome assessment will be strictly blinded.

Process of care outcomes (secondary outcomes): 1) HTN control. Outpatient, sitting BP values measured during each outpatient encounter and recorded in the EHR. BP will be treated as a continuous variable. To minimize ascertainment bias, we will use 6-month ascertainment windows to determine an average BP for each patient for each 6-mo period. 2) Use of RAASi. Will be determined by active use of an ACEi or ARB based on the EHR medication list at each outpatient encounter. Analyses will compare cumulative person-time exposure during the study. 3) Medication safety. We will examine the rates of use of several high-risk medications that can be associated with adverse outcomes in progressive CKD. Medication exposure will be determined by presence of the specified medication on the patient's EHR medication list at each outpatient encounter. Analyses will compare cumulative person-time exposure during the study. a) Use of NSAIDs: use examined for all study patients, b) Use of glyburide: use examined for all diabetic study patients, c) Use of metformin: use examined for diabetic study patients with eGFR<30.

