
**Exploratory analyses:** Although this study is not powered to conduct subgroup analyses, we will perform analyses stratified by age, sex, CKD stage, DM status, HTN with baseline BP (>140/90 mmHg or >130/80 mmHg), and ACEi/ARB in albuminuric patients, or SGLT-2i use to explore whether heterogeneous intervention effects exist among these subgroups. Subgroup by race will also be examined.

Missing Data: The extent of missing data will be described. We will investigate the randomness of

missing data using available information on patient and provider characteristics to identify possible covert missing data mechanisms. The analytical models used can handle data that are missing at random, but other strategies to handle missing data (multiple imputation, selection models, pattern-mixture models) will also be implemented. In addition, adjusted LMM or GLMM will be used to account for variables associated with missingness.

Table 1. Determination of outcomes and covariates based from electronic health record (EHR)

	Determination from EHR	
General principles		
Baseline time point (T0)	Office or telemedicine encounters with the PCP after the date the patient was determined to be eligible will be extracted. The first PCP encounter within 1 year of the date of eligibility determination will be used as the baseline time point (T0).	
Outpatient records	Outpatient data will be extracted from the EHR.     Laboratory results or vital records obtained within a span of 2 consecutive days will be excluded, as these are more likely to stem from inpatient encounters.	
Primary outcome		
Composite of ≥40% decline in eGFR from baseline or ESKD	The CKD-EPI creatinine (2021) equation will be used to calculate eGFR. (6)	

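### The final SAP sets no albuminuric analysis population for RAASi use, so no main secondary analysis estimates the effect that Aim 1b asks about

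*Combined protocol and SAP*

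**What the plan says.** Protocol section III, Study Objectives, gives Aim 1b as: "To examine the effect of the intervention on RAASi use in albuminuric patients". The Study Summary Synopsis words it the same way.

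The Final Statistical Analysis Plan, under process of care outcomes, defines the outcome as: "Use of RAASi. Will be determined by active use of an ACEi or ARB based on the EHR medication list at each outpatient encounter". No population follows. The medication-safety items beside it do name theirs. Two examples are "Use of NSAIDs: use examined for all study patients" and "Use of metformin: use examined for diabetic study patients with eGFR<30"; the glyburide item is limited to diabetic patients.

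The model in the secondary outcomes section is: "In examining medication use, we will compare the average medication exposure days between the arms using LMM with random practice effect". Neither that section nor SAP Table 1, which sets the exposure-day rules by drug class, applies an albuminuria filter.

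The two ideas come together only under Exploratory analyses, in a list of subgroup factors that ends "ACEi/ARB in albuminuric patients, or SGLT-2i use to explore whether heterogeneous intervention effects exist among these subgroups". That paragraph opens: "Although this study is not powered to conduct subgroup analyses".

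SAP Table 1 derives a baseline UACR with a two-year look-back, converted from protein-creatinine ratio or dipstick where needed. No cut-off for being albuminuric appears in the protocol or the SAP.

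**The concern.** An analyst who follows the SAP text would apply no filter and would estimate the RAASi effect in everyone enrolled. Entry does not require albuminuria: protocol Table 1 admits patients on an eGFR of 15-29 alone, or on rapid decline alone. The cohort may therefore contain many patients outside the Aim 1b population.

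The protocol's own rationale ties RAASi to albuminuric or proteinuric CKD (Introduction), and its dashboard example is patients with albuminuria who are not on RAASi. On that logic the effect could well be concentrated in albuminuric patients. A whole-cohort estimate would then understate it, and a real improvement in the target group could be reported as null. Even with no dilution, the pooled estimate answers a different question from the stated aim.

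**Working it through.** **1. The plan's own figure.** The SAP sample-size section gives two-sided alpha 0.05, ICC 0.01, 19 patients per practice, 20% attrition, N = 1,653, and at least 80% power for a standardised difference of 0.2. For RAASi this is 78/390 person-years = 0.20. I assume 1:1 allocation.

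- Design effect = 1 + (19 - 1) x 0.01 = 1.18.
- Effective n after attrition = 1,653 x 0.8 / 1.18 = 1,322.4 / 1.18 = 1,120.7.
- Power = Phi(0.2 x sqrt(1,120.7)/2 - 1.96) = Phi(1.39) = 92%.

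The same formula gives 96% without attrition, and 91% after attrition in the 96% of the cohort expected to have hypertension. The stated power is reproduced for the whole cohort. It says nothing about albuminuric patients.

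**2. The albuminuric subset.** The share a is not in the documents, so I use 0.7, 0.5 and 0.3 as assumptions. After filtering, a practice contributes about 19a patients, so the design effect is 1 + (19a - 1) x 0.01. The detectable difference at 80% power is 2.80 x 2 / sqrt(effective n).

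| a | Design effect | Effective n | Detectable difference | Power at 0.2 |
|---|---|---|---|---|
| 0.7 | 1.123 | 925.7/1.123 = 824 | 0.195 | 82% |
| 0.5 | 1.085 | 661.2/1.085 = 609 | 0.227 | 69% |
| 0.3 | 1.047 | 396.7/1.047 = 379 | 0.288 | 49% |

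The stated 80% at 0.2 carries over to this subset only if a is about 0.66 or more.

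**3. Whole cohort, effect confined to albuminuric patients.** The mean difference shrinks to a times its subset value and the sample grows by 1/a. With a common SD and an unchanged design effect, the test statistic is sqrt(a) times the subset statistic. Starting from 80% power in the subset, whole-cohort power = Phi(2.80 x sqrt(a) - 1.96):

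- a = 0.7: Phi(0.38) = 65%
- a = 0.5: Phi(0.02) = 51%
- a = 0.3: Phi(-0.43) = 34%

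Using the smaller subset design effect replaces sqrt(a) by sqrt(a x design effect / 1.18), that is 0.816, 0.678 and 0.516. Power is then about 63%, 48% and 30%, so the message is unchanged.

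Starting instead from a true difference of 0.2 in albuminuric patients only, the whole-cohort difference is 0.2a = 0.14, 0.10 or 0.06. Power is 65%, 39% or 17%, against 82%, 69% or 49% in the subset.

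**4. Whole cohort, effect equal in both groups.** There is no dilution. Power at 0.2 is 92% in the whole cohort, against 82%, 69% or 49% in the subset.

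**The case against.** The strongest reply is that the SAP never says the RAASi comparison is made in all patients; that is inferred from silence. Its secondary-outcomes section is labelled as Aim 1, and it does not repeat the hypertensive population of Aim 1a for blood pressure either. A reader could carry the aim populations forward. This stands as far as it goes: a reader might infer that the SAP explicitly chose the whole cohort, and it does not. But the populations named for NSAIDs, glyburide and metformin make an unrestricted comparison the natural reading. For Aim 1a the omission matters little, because 96% are expected to qualify; no such figure is given for albuminuria.

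A second reply is that the exploratory list already covers the albuminuric analysis. The wording is ambiguous. It sits among stratifiers such as age, sex and CKD stage, and the original SAP had plain RAASi use in its list of stratifiers, so baseline ACEi/ARB use as a subgroup factor is the likelier meaning. On the kinder reading, a stated aim has become an exploratory analysis without declared power, and without a cut-off it could not be run reproducibly.

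A third reply is that dilution is not shown. This is correct. The nephrology e-consult addresses blood pressure and RAASi use together, so the effect might be similar with and without albuminuria. In that case restriction only loses power.

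**Conclusion.** The concern holds as a mismatch between a stated aim and its analysis. No main secondary analysis is specified for RAASi use in albuminuric patients, that population is not defined, and the power statement does not address it.

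Two stronger readings are tempting and are not supported. One is that the effect is diluted: this needs a smaller effect in non-albuminuric patients, which the documents do not establish. The other is that the documents rule out any albuminuric RAASi analysis: the exploratory wording is too unclear for that.

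The size is conditional. With the effect confined to albuminuric patients and assumed shares of 0.7, 0.5 or 0.3, 80% power in the subset corresponds to about 65%, 51% or 34% in the whole cohort; with equal effects the loss is zero. The point affects one secondary process outcome and leaves the primary endpoint untouched. It should be corrected because the remedy is cheap.

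**What to change.** - Define albuminuric by a stated cut-off on the baseline UACR already derived in SAP Table 1, and say how patients with no usable urine measure are handled.
- Run the existing exposure-days model in that set as the Aim 1b analysis, and report the whole cohort alongside it.
- Restate the detectable standardised difference from the actual share and the recalculated design effect: about 0.20, 0.23 or 0.29 for shares of 0.7, 0.5 or 0.3.
- Reword the exploratory item so that it is clear whether ACEi/ARB is a stratifier or an outcome.
- Label the change post hoc. The SAP's Summary of Major Revisions records that initial results were disclosed to the research team in March 2023.
- If only the whole cohort is analysed, say so and do not present the result as answering Aim 1b.

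The cost is one definition, one filter and some SAP wording. The downside is a smaller sample, with a detectable difference worse than the stated 0.2 when the share is below about 0.66. If the effect is in fact equal in both groups, the restricted analysis also has less power than the whole-cohort one, which is a reason to report both.
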